### Figure 5: Open label phase study flow

- Subjects will operate the device along with the dedicated mobile application independently at home or surrounding, according to the recommended treatment regimen provided by the central trainer and on the “Relivion®DP quick guide” for 8±1 consecutive weeks. The Relivion®DP device programmed treatment duration will be 40 minutes. If needed, (i.e. for originally sham subjects who are not used to the active stimulation sensation) the daily treatment (duration and intensity) will be gradually increased up to a full effective treatment according to the assigned treatment regimen (i.e. for remitters, responders and non-responders). In general, it is expected that the responders and non-responders’ subjects recommended daily treatment time of 60±20 minutes would be performed in two equal time sessions per day (e.g. morning and evening, each of about 30±10 minutes). The remitters subjects would apply the stimulation once a day 3-4 times a week for 40+10 minutes. If necessary, treatment can be paused by the subject and then be resumed. Subjects will continue their assigned treatment regimen up to their scheduled visit 5 day. At study visit 5 the subjects response to treatment, according to HDRS, will be re-evaluated and treatment regimen may be amended accordingly (see Figure 5), re-training will be performed by central trainer, if required. The subjects will continue their assigned treatment regimen up to their scheduled visit 6 day (end of study).
- Subject will continue to self-complete the QIDS-SR-16 once every 7 days.
- The characteristics of each subject assigned study treatments regimen, both from visit 4 and visit 5 (if applicable), will be indicated on the subject binder.
- Study central trainer will periodically verify device logs on the study cloud database and may contact the subject for re-training, if required.
- Study team and central trainer will contact the subject periodically to troubleshoot any issue, If necessary.
- During this period, subject will be asked to schedule 2 follow-up evaluation visits (on-site or remote).

#### 9.1.7. Visit 5 – 12 weeks Follow up (Day 84±7)

Written below are the assessments to be completed at Visit 5 (either on site or remotely):

- Depression symptoms questionnaires:
  - By site qualified rater: HDRS21 (HDRS17- removing 4 last questions from the HDRS21), MDRS, CGI-S & CGI-I
  - By subject: QIDS-SR-16. Subject self-reported questionnaire may be filled in electronically (ePRO) or by hard copy.
- The subjects’ response to treatment, according to HDRS, will be re-evaluated and treatment regimen may be amended accordingly as specified in section 9.1.6 and Figure 5.
- The central trainer will provide training to the subjects on the newly assigned treatment regimen, if applicable.
- Clinically significant current suicidal intent re-assessment by the investigator team (C-SSRS)
- Change in concomitant medications will be documented.
- Adverse events will be documented.

 Neurolief Brain Innovation	MOOD: CLINICAL INVESTIGATION PLAN	Doc No.: CL-CIP-201 Rev: REV.3 / 09June2021 Pg. 51 of 92
--	--	--

### 9.1.8. Visit 6 – end of study (Day 112±7)

Written below are the assessments to be completed at Visit 6 (either on site or remotely):

- Depression symptoms questionnaires:
  - By site qualified rater: HDRS21 (HDRS17- removing 4 last questions from the HDRS21), MDRS, CGI-S & CGI-I
  - By subject: QIDS-SR-16, Q-LES-Q. Subject self-reported questionnaire may be filled in electronically (ePRO) or by hard copy
- Clinically significant current suicidal intent re-assessment by the investigator team (C-SSRS)
- Change in concomitant medications will be documented.
- Adverse events will be documented.
- Subject Impression will be documented by the Subjects Impression Questionnaire.
- Central trainer will arrange the collection of the device and the iPhone, if applicable, from the subjects and final accountability will be performed.
- The summary of each subject study treatments will be indicated on the subject binder.
- At this point subject's participation in this study will be over.
- Adverse Events that are still ongoing will be followed according to section 9.9

## 9.2. Activities Performed by Sponsor's Personnel

A sponsor representative, such the study manager/monitor may be present at the clinic for overseeing and guiding the study screening, enrollment and follow up procedures.

The representatives' activities will occur in such a way that they do not influence the conduct of the study, nor do they interfere with any medical decisions or bias the data integrity. Additionally, they will be described in the Informed Consent Form (ICF) and sponsor technical support list.

Device management and training will be conducted on a centralized fashion by the study qualified and dedicated central trainers. The central trainers' responsibilities may include:

- Operational duties such as: Dispensing of the blinded Relivion®DP devices to the subjects according to the randomization scheme and arranging their collection back to sponsor.
- Following up on subject's treatment compliance throughout the study
- Presence at study visits (on site or remotely) for supporting the study participants in device training and operation.
- Presence at the clinic/remotely for observing the use of the device and gathering information and feedback from the site personnel.
- Arrange the conversion of the Sham devices to Active ones at the start of the OL extension.
- Provide device technical support to subject throughout the study conduct.

 Neurolief Brain Innovation	MOOD: CLINICAL INVESTIGATION PLAN	Doc No.: CL-CIP-201 Rev: REV.3 / 09June2021 Pg. 52 of 92
--	--	--

### 9.3. Prior and Concomitant Medications

Prior to study enrollment visit, subjects will be on a stable dose of Antidepressant medications (type and dose) for at least four weeks, as per subjects' medical records or subject self-report. During the study period, the subject will continue his/her Antidepressant medication treatment on the same type and dose throughout the study. Please see section 9.7 for additional details. During every study visit, the study team will document patient's Antidepressant medication (type and dose).

### 9.4. Subject Consent

Informed consent will be obtained before any study-specific procedures are initiated or data collected. Principal Investigator or his/her authorized designee will conduct the informed consent process.

At the screening visit, subjects will be approached to obtain written or electronic informed consent prior to any data collection. Once the ICF is collected, screening of subject will follow. The purpose of the study and the benefits and risks of the procedures will be explained to the subject and the consent process must be documented accordingly in the medical record. Subjects who agree to study participation must sign a Sponsor and IRB/EC-approved ICF. Consent to participate in this study must be given in writing or electronically. Subjects that are unable to give consent will not be included in study.

Informed Consent will be obtained in accordance with the CFR Title 21, Part 50 (US) or ISO14155:2011 (Israel) as well as the Declaration of Helsinki and will follow the FDA guidance for the use of electronic informed consent.

Electronic measures in order to obtain informed consent remotely will be supplied to all study sites and will be implemented in the study EDC system with accordance to the FDA guidelines for the use of Electronic Informed Consent [37]

The Investigator or designee must obtain written/electronic informed consent before any clinical study related activity takes place. Prior to entry into the study, the IRB/EC and Neurolief-approved ICF form, and the Health Insurance Portability and Accountability Act (HIPAA) Authorization Form (US only) will be given to each subject. The Investigator or designee will fully inform the subject of all aspects of the clinical study that are relevant to the subject's decision to participate in the clinical study (e.g. purpose and duration of the study, requirements of the subject during the study, potential risks and possible benefits associated with participation in this study). All items addressed in the Informed Consent Form must be explained. The language used shall be as non-technical as possible and must be understandable to the subjects.

The subject must have ample time and opportunity to read and understand the Informed Consent Form, to inquire about details of the clinical study, and to decide whether or not to participate in the clinical study. All questions about the clinical study should be answered to the satisfaction of the subject. In the case that a subject is unable to read, an impartial witness must also be present and sign the informed

 Neurolief Brain Innovation	MOOD: CLINICAL INVESTIGATION PLAN	Doc No.: CL-CIP-201 Rev: REV.3 / 09June2021 Pg. 53 of 92
--	--	--

consent to confirm that the research has been clearly explained and all of the subject's questions have been answered.

Neither the Investigator, nor the investigation site staff shall coerce or unduly influence a subject to participate or to continue to participate in the clinical study. The informed consent process shall not waive or appear to waive the subject's rights.

When the subject decides to participate in the clinical study, the HIPAA Form (US only) and the Informed Consent Form must be personally signed and dated by the subject.

After all persons have signed and dated the Informed Consent Form, the Investigator or designee must provide the subject with a copy.

Neurolief will inform the Investigators whenever information becomes available that may be relevant to the subject's confirmed participation in the clinical study. The Investigator or his/her authorized designee should inform the subject in a timely manner.

Neurolief will revise the written Informed Consent Form whenever new information becomes available that may be relevant to the subject's confirmed participation in the clinical study. The revised information will be sent to the Investigator for approval by the IRB/EC. After approval by the IRB/EC, a copy of this information must be provided to the participating subjects, and the informed consent process as described above needs to be repeated.

If the ICF is amended during the course of the study, the IRB/EC will determine:

- Whether or not active subjects should be re-consented at their next visit and
- Whether or not subjects who have completed the study at the time of the amendment should repeat the informed consent process.

Subjects will be informed that qualified personnel from the investigational center, the Sponsor (Neurolief), agencies such as the FDA/local regulatory authority in Israel and/or the IRB/EC may have access to clinic records that reveal their identity.

The investigational center must report the following deviations to their IRB/EC:

- Failure to obtain informed consent from subject.
- Failure to obtain informed consent prior to performing one or more study procedures.
- Failure to maintain ICFs on file for all subjects who have provided informed consent.
- Use of an ICF that has not received approval from the IRB/EC.
- Use of an incorrect version of the ICF.

 Neurolief Brain Innovation	MOOD: CLINICAL INVESTIGATION PLAN	Doc No.: CL-CIP-201 Rev: REV.3 / 09June2021 Pg. 54 of 92
--	--	--

## 9.5. Randomization, Treatment Assignment and Blinding

Subjects will be prospectively randomized into the clinical study. Randomization will occur only after the subject provides informed consent, completes all required screening and baseline procedures, and satisfies the study eligibility criteria. Eligible subjects will be randomly allocated (with a 1:1 ratio) to one of the following 2 treatment groups based on a randomization scheme using the permuted block method stratified by center:

- Active stimulation.
- Sham stimulation.

The randomization scheme will be prepared by the study statistician using the SAS (version 9.4.) random number procedure. The block size will be random, and all study personnel will therefore be blinded to the randomization block size. Only the unblinded statistician /sponsor unblinding party and designates will be privy to the masked randomization scheme.

The Relivion®DP Active and Sham devices will look the same and will be provided in the same packaging bearing the same labeling. Hence, both subjects and study personnel will remain blinded to the assigned treatment group.

## 9.6. Unblinding

### 9.6.1. Planned Unblinding

Subjects and study personnel may be unblinded to each subject's group assignment at the end of the study. Blinding will be opened, and the subject will be notified about his/her treatment assignment, if requested.

### 9.6.2. Unplanned Unblinding

The investigator, sponsor or regulatory authorities may initiate unplanned unblinding procedures in the interest of patient safety.

In case of medical emergency, the Investigator will contact the Sponsor's on call unblinded biostatistician and the specific patient's code will be broken. In case the sponsor's on-call unblinded biostatistician cannot be reached, the investigator will contact the unblinded sponsor representative and the specific patient's code will be broken. The Investigator will promptly document the reason for breaking the code.

## 9.7. Medication Compliance

For the double-blind phase duration, subjects will be asked to maintain on a stable type and dose of antidepressant medications (any psychotropic medications with CNS effects that are prescribed or taken for MDD symptoms).

 Neurolief Brain Innovation	MOOD: CLINICAL INVESTIGATION PLAN	Doc No.: CL-CIP-201 Rev: REV.3 / 09June2021 Pg. 55 of 92
--	--	--

A change of up to 25% (increase or decrease) in dose of an ongoing psychotropic medication would be considered as “no change” i.e stable dose.

A change in the type of an ongoing psychotropic medications and/or discontinuation of medication regimen or a change of dose over 25% (decrease or increase) of an ongoing psychotropic medication throughout the study, would be considered as a “change” i.e. non stable-dose.

If necessary (i.e. In the case of emergence or worsening of insomnia), benzodiazepines  $\leq$ 3mg lorazepam (or equivalent dose of another benzodiazepine) may be used for agitation/anxiety or insomnia up to 3 times per week. Partial benzodiazepine agonists, including zolpidem 5 to 10 mg/day, zaleplon 5 to 10 mg/day, and eszopiclone 2-3 mg/day, may be used on an exceptional basis for insomnia/sleep disturbance within the prescribing doses for insomnia. Any equivalent short half-life non-benzodiazepine hypnotic may be substituted if zolpidem, zaleplon, or eszopiclone are not available.

During the open label phase ineffective antidepressant doses may be decreased, as per investigator discretion.

## 9.8. Assessment of Efficacy

Efficacy parameters including Hamilton Depression Rating Scale -HDRS17 and HDRS21; Montgomery-Asberg Depression Rating Score (MDRS); Quick Inventory of Depressive Symptomatology -QIDS-SR-16; and Clinical Global Impression scales -CGI-S and CGI-I; will be performed and documented at each visit.

The study questionnaires will be documented by a qualified rater (HDRS, MDRS), C-SSRS, CGI-S and CGI-I using the hard copy questionnaires and thereafter will be documented in the subject’ CRF.

The study questionnaires that are self- reported by the subjects (QIDS-SR-16, Q-LES-Q, SIQ) will be completed using the study EDC ePRO tool or hard copy.

The treatment duration and intensity will be documented automatically in the device logs.

## 9.9. Assessment of Safety

Safety will be assessed by the collection of adverse events information from Enrollment through study exit. Type, incidence, severity, duration, and procedure/device relationship of adverse events (AEs) will be collected throughout the study. Subjects with AEs at study exit will be followed for 14 days or until event resolves, whichever comes first. Adverse event data will be collected and reported on eCRFs.

Additionally, at baseline and during each visit (from randomization throughout the study) and whenever there is a suspect for increased suicidal intent, the investigator team will perform the Columbia-Suicide Severity Rating Scale (C-SSRS) questionnaire with the subject for the assessment of suicidality. At baseline, subjects that in the past 12 months reported active suicidal intent or plan as defined by a “yes” answer to

 Neurolief Brain Innovation	MOOD: CLINICAL INVESTIGATION PLAN	Doc No.: CL-CIP-201 Rev: REV.3 / 09June2021 Pg. 56 of 92
--	--	--

Q4 or Q5 on C-SSRS questionnaire or had a history of suicide attempt in the past twelve months will be excluded (according to exclusion criteria # 12). Throughout the study, an answer of "yes" to Q 4 or Q5 would serve as an immediate need for re assessment with the principal investigator. Upon principal investigator assessment of the "yes" answer to Q4 or Q5, the patient would be excluded from the study and the event will be reported as an AE.

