### **5.1.7. Safety Endpoint**

Safety of the study device following study treatment: Incidence of adverse events and serious adverse events related or unrelated to the study device [Time Frame: up to 18 weeks post treatment initiation].

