## 10.3. Risk Control and Mitigation

The following efforts will minimize risks to subjects in the study:

- Conduct of the study following successful completion of extensive bench performance testing and careful risk analysis.
- Selection of investigators who are experienced and skilled in management of patients with MDD.
- Establishment of a training program for study staff members (investigators and coordinator) and use of tools that will ensure proper training to the subjects for home use of the device.
- Clearly defining the inclusion and exclusion criteria such that only appropriate patients are enrolled in the study.
- Close monitoring of worsening of depression symptoms and suicidal intent

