## 11. Adverse Events and Device Deficiencies

Adverse event definitions used in this study are based on ISO 14155:2020 (Clinical Investigation of Medical Devices for Human Subjects -- Good Clinical Practice).

 Neurolief Brain Innovation	MOOD: CLINICAL INVESTIGATION PLAN	Doc No.: CL-CIP-201 Rev: REV.3 / 09June2021 Pg. 61 of 92
--	--	--

Adverse Events will be collected for all enrolled subjects with the point of enrolment (Visit #2 upon randomization) and end at the study termination visit (visit #6). Subjects with AEs at termination visit will be followed for 14 days or until event resolves, whichever comes first.

During the course of the study, all AEs will be collected and reported on the CRF/eCRF including:

- All AEs related to Relivion®DP device and/or procedure.
- All AEs not related to Relivion®DP device and/or procedure.
- All device deficiencies that may lead to a SAE.
- All Deaths

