**Adverse Event Outcome Classification**

Adverse Event Outcome Classification will be defined according to the following:

**Resolved:** The event has fully resolved at the end of the study.

**Resolved with sequel:** The event has resolved, but retained pathological conditions resulting from the prior disease or injury.

**Continuing:** The event is ongoing at the end of the study.

**Death:** This event is determined to be the cause of death.

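### The 14-day limit on AE follow-up after exit (Protocol 9.9) makes no exception for SAEs or C-SSRS Q4/Q5 events, so a subject excluded at Day 28 has required follow-up only to about Day 42

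*Protocol*

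**What the plan says.** Protocol 9.9 sets the general rule: "Subjects with AEs at study exit will be followed for 14 days or until event resolves, whichever comes first". Section 11 repeats it for the end of the study: "Subjects with AEs at termination visit will be followed for 14 days or until event resolves, whichever comes first". There the termination visit is identified as Visit 6. The Visit 6 procedures in 9.1.8 add nothing of their own: "Adverse Events that are still ongoing will be followed according to section 9.9".

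Protocol 9.9 also says what happens when a subject answers 'yes' to C-SSRS Q4 or Q5 during the study. The principal investigator re-assesses at once, and on that assessment "the patient would be excluded from the study and the event will be reported as an AE". C-SSRS is given at baseline, at each visit from randomization on, and "whenever there is a suspect for increased suicidal intent". The text does not say whether that last trigger continues after a subject has left.

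The safety endpoint in 5.1.7 has a time frame of "up to 18 weeks post treatment initiation". Section 10.3 lists among the risk controls: "Close monitoring of worsening of depression symptoms and suicidal intent".

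**The concern.** Section 10.1 acknowledges that sham assignment may let depression worsen, suicidal intent included. The scheduled controls against this (HDRS, the weekly QIDS-SR-16, and C-SSRS at visits) run through study participation. Exclusion ends that participation, and from then on the only stated follow-up duty is the 14-day rule. For the subjects in whom the named risk has actually appeared, the study's monitoring duty therefore shortens.

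SAEs fall under the same rule. An SAE still open 14 days after exit need not be pursued further under 9.9.

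At stake is the welfare of those subjects and a complete account of a few important events. No efficacy result is at stake.

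**Working it through.** **Inputs.** Visit days and windows from Table 1 and 9.1: Visit 3 Day 28±7, Visit 4 Day 56±7, Visit 5 Day 84±7, Visit 6 Day 112±7. Limit from 9.9: 14 days. Safety time frame from 5.1.7: 18 weeks.

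**Reproducing the plan's own figure.** 18 weeks × 7 = 126 days. Visit 6 plus the limit is 112 + 14 = 126. The two agree exactly at the nominal day, so the 14-day rule suits completers.

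**Last day of required follow-up = exit day + 14.**

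| Exit at | Exit day (window) | Last required day (window) | Days short of Day 126 at nominal exit |
|---|---|---|---|
| Visit 3 | 28 (21–35) | 42 (35–49) | 126 − 42 = 84 |
| Visit 4 | 56 (49–63) | 70 (63–77) | 126 − 70 = 56 |
| Visit 5 | 84 (77–91) | 98 (91–105) | 126 − 98 = 28 |
| Visit 6 | 112 (105–119) | 126 (119–133) | 0 |

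Over the Visit 3 window the shortfall runs from 126 − 49 = 77 to 126 − 35 = 91 days. The table assumes exit on the visit day. Re-assessment by the principal investigator comes first, so the true exit may be slightly later.

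**Is there an exception elsewhere?** These provisions come closest:

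- 9.12 asks for an attempted exit visit and sets no later contact.
- 10.1 tells subjects and family to contact the study doctor if symptoms worsen. The initiative lies with them.
- 11.3.5 makes updates to reported events reportable, but does not require anyone to seek them.
- 11.3.7 provides a narrative and adjudication for SAEs and device effects, and lets the sponsor ask for more information. A Q4/Q5 event that is neither serious nor device-related would get no narrative under this text.
- 11.3.7 and 14.1 give the DMC periodic safety data and let it recommend changes.
- 14.12 provides standard-of-care follow-up when the whole investigation stops, not when one subject is excluded.
- The SAP repeats the 18-week time frame and adds no follow-up rule.

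None of these requires contact with the subject after day 14.

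**How many subjects?** The documents give no rate for a Q4/Q5 'yes' and none for SAEs; the 23-subject feasibility study saw no SAE. Purely as an assumption, take 1% to 5% of 126 subjects (124 adults plus the two under 22 mentioned in SAP 10.4). That gives 0.01 × 126 = 1.26 to 0.05 × 126 = 6.3, or about 1 to 6 exclusions. Only those still unresolved at day 14 would be affected, which could be none.

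**The case against.** The strongest reply is that the rule is deliberate, appears in the same form in 9.9 and 11, matches the safety time frame, and sets only a minimum. It limits what the study must do, not what a clinician may do. Subjects stay on their antidepressants, and when depression worsens the team can unblind and change treatment at once (10.1). The sponsor can ask for further information with no time limit, and the DMC sees the safety data. Exclusion criterion 12 removes anyone with intent, a plan or an attempt in the previous 12 months, so few events should arise. All of this stands, and it keeps the point modest. It does not supply a duty to check on an excluded subject after day 14.

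Three stronger readings are tempting and should be resisted.

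- A reader might cite section 11 as well as 9.9 for the Day 28 case. Section 11 ties its limit to Visit 6, so only 9.9 governs an early exit.
- A reader might infer that a site may close an open event as 'Continuing' on day 14. The outcome classification under 11.3.3 defines that category as "The event is ongoing at the end of the study", and does not tie it to 14 days after an individual's exit. Table 1 does mark Visit 4 as end of study for non-compliant subjects, so the wording is ambiguous for early exits, but it does not say this.
- A reader might conclude that the safety analysis is compromised. The safety endpoint is incidence, and the primary safety variable is the cumulative incidence of device-related AEs. An event open at exit is already counted, however it ends.

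**Conclusion.** The point holds as a gap in required safety follow-up. Under 9.9, a subject excluded for a Q4/Q5 'yes' at Visit 3 has required follow-up to about Day 42 (35 to 49), which is 84 days (77 to 91) short of the Day 126 reached by a completer. SAEs open at exit are under the same limit. This rests on the subject being excluded as 9.9 directs, on exit at or near the visit day, and on the event being unresolved at day 14.

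AE and SAE incidence and every efficacy analysis are unaffected. What is lost is monitoring of the subject and the later course and final outcome of a few events. Their number is unquantified and may be zero. The change is worth making because it concerns a risk that the protocol itself names and because it is cheap. It is not a condition for the trial's validity.

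**What to change.** In 9.9, and in section 11 for Visit 6, exempt two groups from the 14-day limit: SAEs, and C-SSRS Q4/Q5 suicidality events. Name the second group explicitly, because 9.9 records these only as AEs and they may not meet the SAE definition in 11.1.

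Follow both groups until the event is resolved, stable or under documented care elsewhere. Set an outer bound so that the duty is not open-ended, for example Day 126 or 30 days after exit, whichever is later. For a Day 28 exit this is Day 126, since 28 + 30 = 58 is earlier. For a Day 112 exit it is 112 + 30 = Day 142. Contact can be remote and with the subject's agreement; the study visits already allow remote conduct. All other AEs, including non-serious skin redness or tingling, keep the 14-day rule.

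The cost is a few sentences in two sections and a few extra remote contacts for a few subjects. The downside is that those subjects are contacted for longer after they have left the study.
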